#### **Other Outcomes**

- Use of platelet transfusions: The difference in number of platelet units administered will be compared between the intervention groups up to death/end of chemotherapy cycle (whichever comes first).
- Ability of participants to remain blinded to the transfusion threshold

#### 9.3 Sample size

This is a feasibility study that will help in planning a larger definitive trial. We propose a sample of 36 patients (who complete a period of observation for one full cycle of chemotherapy) to determine feasibility in the UK. Power calculations based on a two-sided paired t-test indicated that a sample size of 31 patients can achieve 90% power to detect a 15 g/L difference between the two transfusion strategies. We assumed the estimated group standard deviation of 20g/L (informed by the Carson et al 2012 Cochrane systematic review of red cell transfusion thresholds), an intra-class correlation coefficient of 0.25 and a significance level of 0.05. After allowing for a drop-out rate of 10%, and rounding up to an even number to ensure the same number are assigned to each randomisation schedule, the total sample size will be at least 36 patients.

#### 9.4 Analysis Plan (brief)

The analyses will be described in detail in a full Statistical Analysis Plan. This section summarises the main issues.

Appropriate statistical methods for the analysis of cross-over trials will be used. These may include mixed-effects models with a random effect for participant, paired methods or another suitable method, with adjustment for any period effect between cycles. The primary analysis will be performed according to intention to treat.

Data from all randomised participants who have received any transfusions will be included in the 'compliance to treatment threshold' analysis. Percentage compliance of pretransfusion haemoglobin concentrations being **below** the target range of the RBC transfusion threshold assigned will be presented by allocation arm. The percentage of pretransfusion haemoglobin concentrations falling below, within and above the target range will also be presented by allocation arm. The proportion of transfusions, proportion of participants and proportion of transfusions per participant given correctly, according to the algorithm, will also be calculated for each allocation arm.

The mean pre-transfusion haemoglobin level for each participant (regardless of whether they received a transfusion) will be calculated for each course of chemotherapy, then 2 overall means will be calculated for the restrictive and liberal groups, and the difference determined, looking for at least a 15g/L difference.

We will consider this study feasible and worthy of further development into a larger randomised trial if compliance for adherence is ≥70% in both arms. This will be reported by calculating the percentage of haemoglobin measurements that fall within or above their assigned target range pre- transfusion.

For analysis of other measures of feasibility, all patients who are eligible and ineligible will be documented and the proportion of randomised patients noted. Those who consented to and were enrolled in the trial will be analysed, even if they did not receive any transfusions, to understand reasons for failure to complete the assigned strategy.

Participants who completed QoL questionnaires will be included in the QoL analysis. The minimum required number for this analysis is completed QoL questionnaire at baseline, and after one chemotherapy cycle The percentage compliance with completing the QoL questionnaires will be summarised for each arm and each timepoint.

The mean EQ-5D-5L and EORTC QLQ C30 scores for each arm will be calculated and compared at baseline and after each chemotherapy cycle. Clinically meaningful improvement will be defined as ≥0.08 on the calculated health utility EuroQOL-5D score and ≥10 points on the EORTC QLQ-C30 score (for all scores apart from fatigue and dyspnoea, for which an improvement is ≤-10). In addition to aggregate data, the percentages of participants individually achieving a clinically meaningful improvement, at any time point, compared to the baseline score (the first QoL questionnaire at randomisation), in each of the two strategies will be compared.

For other and safety analyses, data from all randomised subjects will be evaluated and descriptive statistics presented. Key clinical characteristics of enrolled participants will be compared against all recruits to AML 18 and 19 trials. The extent of exposure will be summarised (median RBC and platelet units transfused during each chemotherapy course), as well as the clinical course, such as interval between transfusions and transfusion reactions. The incidence of WHO Grade 3 or 4 bleeding and death will be summarised by treatment strategy, and length of hospital stay compared. Comparisons will be made between the two haemoglobin concentration threshold transfusion strategies. Any adverse events potentially related to the transfusion threshold such as cardiac ischaemic events, congestive heart failure, strokes (cerebrovascular accidents, CVA), thromboembolic or syncopal events, will be summarised and compared between the two arms.

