	alternative transfusion policy (i.e. if allocated to restrictive arm for cycle 1, this would be the liberal arm for cycle 2
Study hypothesis	It is feasible to achieve adherence when randomising patients to one of 2 haemoglobin thresholds and maintaining haemoglobin concentrations between either 71-80 g/L or 91-100 g/L
Primary outcome measure(s)	
 
Percentage of pre-transfusion haemoglobin concentrations being below the target range of the assigned red cell transfusion strategy
 
Achievement of at least a 15g/L difference between the mean pre-transfusion haemoglobins in the two transfusion groups
 

Secondary outcome measure (s)	Adherence outcomes: transfusions given per protocol, red cell exposure, adherence to outcome monitoring, recruitment rate, characteristics of recruited participants  Clinical outcomes: bleeding, thrombosis, culture verified bacterial infections, platelet transfusion, Quality of Life (QoL), transfusion reactions, death  Monitoring outcomes: compliance with data collection between sites
Duration of Study	
 
Recruitment for 18 months
 
Intervention from diagnosis until end of second cycle or cycle 2 Day +42 i.e. the 42nd day after the last dose of chemotherapy (approximately 3 months)
 
No further follow-up beyond intervention period
 
Duration of trial – 2 years
 

Study Schedule	The study schedule can be found in section 6.1 of the protocol.
Sample Size	36 patients (for one complete cycle of chemotherapy) with equal numbers in each arm
Ancillary Studies/substudies	None
Trial manager	[name]
CTU Project Manager	[name]

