# 5.2 Intervention Arm: Restrictive Transfusion Policy (RBCs transfused when haemoglobin ≤70g/L)

Following enrolment, the haemoglobin values of participants will be recorded according to routine clinical care. If the haemoglobin value is recorded as ≤70 g/L, red blood cells should be transfused at a dose of 1 unit at a time, with the aim of keeping the haemoglobin range between 71-80 g/L. The timing of repeat haemoglobin measurements should be decided by the attending haematologist. Further red blood cell transfusions should only be administered if the haemoglobin value decreases to a value of 70g/L or less (see figure 1). Any transfusion required as part of the policy should be administered within 24 hours of obtaining the haemoglobin result (up to 72 hours for outpatients). For participants with haemoglobin values significantly lower than the threshold (i.e. where one unit would not be expected to increase the haemoglobin level into the desired range) more than 1 unit at a time may be transfused.

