#### 9.2.2 Secondary Outcomes

Overall haemoglobin difference: mean haemoglobin for the liberal and restrictive strategies using all haemoglobins reported.

**Adherence:** These will be measured by determining:

- The proportion of enrolled participants for whom the transfusion policy was successfully followed until the end of that chemotherapy cycle/death, whichever comes first. The transfusion policy will be defined as having been successfully followed if the participant always received a RBC transfusion within the defined time frame when their haemoglobin dropped below the trigger level, and did not receive any RBC transfusions when their haemoglobin was above the trigger level.
- The proportion of enrolled participants for whom the transfusion policy was successfully followed but allowing for one 'violation'.
- The proportion of transfusions per participant that were correctly given according to their haemoglobin trigger (i.e. had a haemoglobin value ≤70 g/L in the restrictive transfusion group and a haemoglobin value ≤90 g/L in the liberal transfusion group).
- The proportion of times a participant received a transfusion contrary to their haemoglobin trigger (i.e. had a haemoglobin value >70 g/L in the restrictive transfusion group and a haemoglobin value >90 g/L in the liberal transfusion group).
- The overall proportion of transfusions that were correctly given according to the participant's haemoglobin trigger (i.e. had a haemoglobin value ≤70 g/L in the restrictive transfusion group and an haemoglobin value less than ≤90 g/L in the liberal transfusion group).
- The overall proportion of times a transfusion was given contrary to the participant's haemoglobin trigger (i.e. had a haemoglobin value >70 g/L in the restrictive transfusion group and an haemoglobin value >90 g/L in the liberal transfusion group).

- The overall proportion of transfusions that were given correctly according to the participant's haemoglobin trigger by whether given as inpatient or outpatient
- The proportion of inpatient and outpatient transfusions given as single or multiple unit transfusions
- Percentages of transfusions performed where the pre-transfusion haemoglobin concentrations fell below, within and above the target haemoglobin range
- Percentages of transfusions performed where the post-transfusion haemoglobin concentrations fell below, within and above the target haemoglobin range

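### The 70% feasibility rule in section 9.4 counts pre-transfusion haemoglobins within or above target, the reverse of the primary adherence outcome, so full adherence to the trigger scores 0% and fails

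*Protocol*

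**What the plan says.** The feasibility paragraph of protocol section 9.4 (its fifth) says the study will be considered "worthy of further development into a larger randomised trial if compliance for adherence is ≥70% in both arms". The next sentence says how that compliance is obtained: by "calculating the percentage of haemoglobin measurements that fall within or above their assigned target range pre- transfusion".

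Elsewhere the protocol counts the other side of the range:

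- **Study Synopsis, primary outcomes:** "Percentage of pre-transfusion haemoglobin concentrations being below the target range of the assigned red cell transfusion strategy". Section 9.2.1 repeats this under the label of adherence.
- **Section 9.4, third paragraph:** percentage compliance is the share of pre-transfusion values below the "target range of the RBC transfusion threshold assigned will be presented by allocation arm".
- **Section 9.2.2:** a transfusion is correctly given if the participant "had a haemoglobin value ≤70 g/L in the restrictive transfusion group", or ≤90 g/L in the liberal group. A transfusion at >70 or >90 g/L respectively is contrary to the trigger.

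Section 5.2 sets out the restrictive policy: "If the haemoglobin value is recorded as ≤70 g/L, red blood cells should be transfused at a dose of 1 unit at a time". The range to be held by these transfusions is 71–80 g/L. Section 5.3 has the same structure for the liberal policy, with a trigger of ≤90 g/L and a range of 91–100 g/L.

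**The concern.** In both arms the target range begins immediately above the trigger. It is where the haemoglobin should be held by transfusion, not where it should be when a transfusion is started. A pre-transfusion value inside or above the range means that the transfusion was given before the trigger was reached. The feasibility sentence counts those values as compliance.

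The ≥70% rule is the only place where the protocol attaches a numerical cut-off to the decision that a larger trial is worthwhile. The 15 g/L separation is also a primary outcome, but 9.4 does not tie the statement on feasibility and further development to it. If the sentence is applied literally, an arm that follows its policy fails and an arm that is mostly transfused off policy passes. If it is quietly reinterpreted, the numerator of the progression rule is chosen after the data are seen.

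**Working it through.** The 70% cut-off is a chosen criterion, so there is no derivation to reproduce. The check is whether the metric attached to it measures adherence. The sample size in 9.3 does not depend on this rule.

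**Inputs**

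| | Restrictive (5.2) | Liberal (5.3) |
|---|---|---|
| Trigger | ≤70 g/L | ≤90 g/L |
| Target range | 71–80 g/L | 91–100 g/L |
| Correct transfusion (9.2.2) | ≤70 g/L | ≤90 g/L |
| Contrary transfusion (9.2.2) | >70 g/L | >90 g/L |

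Haemoglobin is taken in whole g/L.

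**Step 1: place correct transfusions against the range.** Every value ≤70 is below 71, and every value ≤90 is below 91. In each arm, 100% of correctly triggered values are below the range and 0% are within or above it. Conversely, >70 is the same as ≥71, and >90 the same as ≥91. Values within or above the range are therefore exactly the contrary transfusions of 9.2.2.

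**Step 2: relate the two scores.** Let C be the percentage of transfusions in an arm with a pre-transfusion value at or below the trigger.

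- Primary outcome (percentage below range) = C
- Feasibility metric (percentage within or above range) = 100 − C

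**Step 3: apply the cut-off.** The primary-outcome version passes if C ≥ 70. The version in the feasibility sentence passes if 100 − C ≥ 70, that is, if C ≤ 30.

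| C, adherence to trigger | Score as % below range | Result | Score as % within or above | Result |
|---|---|---|---|---|
| 100% | 100% | pass | 0% | fail |
| 90% | 90% | pass | 10% | fail |
| 80% | 80% | pass | 20% | fail |
| 70% | 70% | pass | 30% | fail |
| 50% | 50% | fail | 50% | fail |
| 30% | 30% | fail | 70% | pass |
| 20% | 20% | fail | 80% | pass |
| 0% | 0% | fail | 100% | pass |

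Both arms must pass. One version needs C ≥ 70 in each arm and the other needs C ≤ 30 in each arm, so no result passes both. They agree only in failing: when both arms lie strictly between 30% and 70%, or when the arms differ so that neither version is met in both.

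**The case against.** Four points can be made for the text as it stands.

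*The sentence is only a reporting slip.* The criterion is compliance, which the third paragraph of 9.4 has already described as values below the range, so readers would know what is meant. That is probably the intention. But the sentence directly attached to the cut-off is the one that says how the figure is calculated, and it gives the wrong numerator.

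*The denominator may be all haemoglobin measurements.* The sentence speaks of measurements. The paragraph before it uses a mean pre-transfusion value for each participant whether or not a transfusion was given, and the study hypothesis concerns holding haemoglobin within the ranges. If untransfused measurements counted, within or above could be a maintenance measure and the table above would not follow. This reading fits poorly: the sentence is limited to pre-transfusion values and is offered as the measure of adherence. It would still conflict with the primary outcome.

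*Adherence is wider than the trigger.* Sections 9.2.2 and 5.1 also set time limits, and 9.2.2 counts transfusions that were due but not given. This stands as a limit on the figures: 100 − C describes only the trigger component among transfusions given. Discretionary transfusions above the trigger under section 5.5 would raise the score in the feasibility sentence.

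*The correct figure will be visible anyway.* Section 9.4 also presents the percentages below, within and above range by arm, and a compliance near zero would be noticed. The SAP may use the right numerator. Both reduce the chance of harm, but neither corrects the protocol's stated decision rule, and a SAP that counts values below the range would contradict it.

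**Conclusion.** The concern holds. The metric attached to the ≥70% rule is the complement of the primary adherence outcome, and it counts the transfusions that 9.2.2 treats as contrary to the trigger. Full adherence to the trigger scores 0%, adherence of 70% or more always fails, and the rule is met only when adherence is 30% or less in both arms.

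These figures assume whole-number haemoglobin values, a denominator of transfusions given, and adherence meaning adherence to the trigger alone. The contradiction between the feasibility sentence and the primary outcome rests on none of the last two assumptions. The rule works by arm, so nothing here implies a pass or fail for individual sites. This must be corrected before analysis, because it can reverse the trial's feasibility conclusion.

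**What to change.** In the feasibility paragraph of 9.4, replace the reference to values within or above the range with: *below their assigned target range (≤70 g/L restrictive, ≤90 g/L liberal)*. The ≥70% rule then has the same numerator as the primary outcome in 9.2.1: adherence of 100%, 90%, 80% and 70% passes and 30% fails. State in the same sentence that the denominator is the pre-transfusion values of transfusions actually given, which closes off the all-measurements reading. Confirm that the SAP uses the same numerator and denominator.

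The cost is one sentence in the protocol and one check of the SAP. Transfusion triggers, target ranges, data collection and sample size are unchanged.

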#### 6.4 Procedures for Assessing Quality of Life

Quality of life will be assessed using the EQ-5D-5L and EORTC QLQ C30 questionnaires. These will be completed at consent, at mid point of each cycle and again at the end of each cycle (i.e. D+42 or on commencement of the next cycle). The mid point is defined as the time of nadir cytopenia. In DA regimen, this is day 10-12 post chemotherapy; in FLAG-Ida regimen, this is day 10- 16 post chemotherapy. If the participant is unable to complete the questionnaire, it may be completed by a suitable surrogate (carer or research nurse) and reason for this documented.

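### The QLQ-C30 responder rule reverses direction for fatigue and dyspnoea only, so a 10-point worsening on any other symptom score counts as an improvement

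*Protocol*

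**What the plan says.** Section 9.4 of the protocol sets the QLQ-C30 improvement threshold at a rise of at least 10 points "for all scores apart from fatigue and dyspnoea, for which an improvement is ≤-10". The rule therefore gives a threshold, a default direction and a closed list of two exceptions.

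The rule is then used for a responder analysis, in addition to the aggregate scores. The two strategies are to be compared on "the percentages of participants individually achieving a clinically meaningful improvement, at any time point, compared to the baseline score".

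Nothing limits which scores this covers. The same paragraph opens with "The mean EQ-5D-5L and EORTC QLQ C30 scores for each arm will be calculated and compared at baseline and after each chemotherapy cycle", section 6.4 says "Quality of life will be assessed using the EQ-5D-5L and EORTC QLQ C30 questionnaires", and section 9.2.3 lists health-related quality of life by instrument. None of these places names a subset of scales. No part of the protocol gives a scoring key or says that any symptom score is reversed before analysis.

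**The concern.** A fall counts as improvement for fatigue and dyspnoea only if those scores are kept in the direction where a higher value is worse. The questionnaire's other symptom scores should then run the same way. As written, they take the default direction, so a participant whose pain or nausea score rises by 10 points is a responder and one whose score falls by 10 points is not.

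Two features of the plan make this more than a slip in wording:

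- **Any time point is enough.** A single qualifying rise from baseline makes a participant improved. Section 6.4 places one assessment at the nadir of cytopenia in each cycle, when a temporary rise in symptoms is plausible.
- **Quality of life is part of the case for the trial.** Section 1.3 notes that the earlier feasibility trial in haematological malignancy included no quality-of-life measure, and argues that functional outcomes and symptoms are likely to matter more in these patients. Section 9.3 says the study is to help plan a larger trial. A responder table with the wrong sign would be a poor basis for that.

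**Working it through.** There is no stated figure to reproduce, because the question is the sign of a rule. The check applies the rule as written and then shows what the sign does to a responder percentage.

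**Inputs from the protocol (section 9.4).** Improved if change ≤ −10 for fatigue and dyspnoea; improved if change ≥ +10 for every other QLQ-C30 score. Change is measured from baseline.

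**Assumption.** All symptom scores run higher = worse; global health and the functional scales run higher = better. The protocol does not state this in full, but its own treatment of fatigue and dyspnoea is consistent with it.

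**Step 1: the rule as written.**

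| Score | −20 | −10 | 0 | +10 | +20 |
|---|---|---|---|---|---|
| Fatigue, dyspnoea | improved | improved | no | no | no |
| Pain, nausea, insomnia | no | no | no | improved | improved |

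The first row is right for a score where higher is worse. The second row is the reverse of what it should be.

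**Step 2: how many scores are affected.** Under the same assumption there are nine symptom scores: fatigue, dyspnoea, nausea/vomiting, pain, insomnia, appetite loss, constipation, diarrhoea and financial difficulties. Two are reversed, so 9 − 2 = 7 are not.

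**Step 3: size, as an illustration.** Let the change in a symptom score at one time point be normal with mean m and standard deviation s. The protocol gives neither, so s is taken from 15 to 30.

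- Written rule: P(change ≥ 10) = 1 − Φ((10 − m)/s)
- Corrected rule: P(change ≤ −10) = Φ((−10 − m)/s)

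For an average worsening of 10 points (m = +10), the written rule gives 1 − Φ(0) = 50% whatever s is. The corrected rule gives Φ(−20/s): 9.1% at s = 15, 15.9% at s = 20, 21.2% at s = 25 and 25.2% at s = 30. For an average improvement of 10 points (m = −10) the two columns swap.

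**Step 4: effect on the comparison of strategies.** Suppose a symptom worsens by 10 points on average under one strategy and does not change on average under the other.

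| s | Written: worsening strategy | Written: stable strategy | Corrected: worsening strategy | Corrected: stable strategy |
|---|---|---|---|---|
| 15 | 50% | 25.2% | 9.1% | 25.2% |
| 20 | 50% | 30.9% | 15.9% | 30.9% |
| 25 | 50% | 34.5% | 21.2% | 34.5% |
| 30 | 50% | 36.9% | 25.2% | 36.9% |

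In every row the written rule ranks the worsening strategy first and the corrected rule ranks it last. The reversal follows from the sign; only its size depends on the assumed values.

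**The case against.** The best defence is that fatigue and dyspnoea are the symptoms a red cell transfusion trial would choose to study. If the analysis covers only the functional and global scores plus those two, the bracket is correct and no result changes. Section 9.4 is headed as brief and leaves detail to a full SAP. The amendment history in section 16 says that version 2.0 brought section 9 into line with that SAP, so a list of scales may exist there. The protocol does not say so, however, and wording that covers all scores but two does not invite that reading. What stands is that the effect on results is conditional: if the SAP restricts the scales in this way, the harm is confined to the protocol text.

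It is also fair to say that the number and direction of the remaining symptom scores come from the instrument and not from the protocol. That is why they are given here as an assumption. The two reversals in section 9.4 make the assumption hard to avoid.

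Finally, the reach is limited. The scores themselves are not altered, and the comparison of means, the EQ-5D rule, fatigue, dyspnoea and the scores where higher is better are all untouched. The primary outcomes are pre-transfusion haemoglobin measures, and the progression criterion is adherence of at least 70% in both arms. No figure in the protocol shows that symptoms will differ between strategies, so a reversed ranking is a possibility and not a prediction. All of this stands and limits the severity, but it does not make the rule right.

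**Conclusion.** The rule is wrong as written. Followed literally, it labels a worsening of 10 points or more as a clinically meaningful improvement on every symptom score except fatigue and dyspnoea, which is seven of nine under standard scoring. In the illustration, a symptom that worsens by 10 points on average shows 50% of participants improved where 9% to 25% would be correct.

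The conclusion rests on two assumptions: that the other symptom scores run in the same direction as fatigue and dyspnoea, and that the analysis covers the whole questionnaire, as the protocol's wording implies. The percentages rest further on normal changes, assumed means and standard deviations, and a single time point. The error is confined to a secondary quality-of-life responder summary. It should be corrected before that analysis is run, but it does not threaten the trial's main feasibility conclusions.

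**What to change.** In section 9.4, replace the bracketed exception with a rule by type of scale: improvement is a rise of at least 10 points for global health status and the functional scales, and a fall of at least 10 points for all symptom scales and items. This is correct whichever scales are analysed. If only some scales are meant to be analysed, name them in the same sentence.

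Check the derivation in the SAP and the analysis code for the same wording and align them. The cost is one sentence in the protocol and the matching SAP derivation; no further data, participants or assessments are needed.
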